10.3. Clinical Laboratory Evaluations

Clinical Laboratory results will be summarized descriptively for each treatment group by time point for the observed value as well as for the change from baseline value. In addition, laboratory shift tables will be provided for all laboratory parameters where low/normal/high or abnormal/normal status can be ascertained. Listings of individual laboratory parameters by visit with normal ranges and abnormality assessments will also be completed by subject.

10.4. Vital Signs

Vital sign results will be summarized descriptively for each treatment group by time point for the observed value as well as for the change from baseline value. All vital sign data by subject will be presented in a listing. Unscheduled visit results will not be summarized but will be included in subject data listings.

10.5. Physical Examinations

Physical examinations are conducted at baseline. A by subject listing will be completed to display all baseline physical examination information, as well as any optional PE information collected.

10.6. Other Safety Measures

C-SSRS results will be presented in subject data listings.

USP summary scores (stress urinary incontinence score, overactive bladder score, and low stream score) will be summarized descriptively for each treatment group by time point for the observed value as well as for the change from baseline value. All USP data (including the 10 individual questions) will be presented in listings.

ECG parameters will be summarized descriptively for each treatment group by time point for the observed value as well as for the change from baseline value. All ECG data will be presented in listings.

No other safety analyses have been prospectively defined. If, however, after study results are reviewed, or the DSMB or Sponsor recommend additional safety parameters or analyses be completed, they will be fully described and documented in the final clinical study report. The SAP does not need to be amended to complete any other safety measures identified as post-hoc.

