9.6.3 Columbia–Suicide Severity Rating Scale

The C-SSRS will be administered by the investigator or a qualified designee trained in its administration. The C-SSRS is a standardized instrument that was developed to assess the severity of and monitor changes in suicidal ideation and behavior. Four constructs are measured. The first is severity of ideation rated on a 5-point ordinal scale. The second is intensity of ideation, which comprises 5 items (frequency, duration, controllability, deterrents, and reason for ideation) each rated on a 5-point ordinal scale. The third is behavior rated on a nominal scale that includes actual, aborted, and interrupted attempts; preparatory behavior; and non-suicidal self-injurious behavior. The fourth is lethality, which assesses actual attempts; actual lethality is rated on a 6-point ordinal scale, and if actual lethality is zero, potential lethality of attempts is rated on a 3-point ordinal scale.

The C-SSRS assessment will be done at the visits specified in Table 1. The C-SSRS is provided in Appendix 5.

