11.5 Safety Endpoints

Safety endpoints will be reported on the Safety population. Subjects will be reported according to the treatment they actually received. Safety assessment will be based on descriptive statistics and individual subject listings. No statistical tests will be performed for any of the safety assessments.

All reported AEs will be mapped to the Medical Dictionary for Regulatory Activities (MedDRA) system organ classifications (SOCs) and preferred terms (PTs). If a subject reports multiple events of a single PT, the greatest severity and strongest investigator assessment of relationship to study treatment will be assigned to that PT. Summaries of TEAEs will include any AEs reported beginning with the first dose of study treatment on Day 1. The occurrence of TEAEs will be summarized by treatment group using SOCs, PTs, and severity. Separate summaries of treatment-emergent SAEs, TEAEs considered related to study treatment, and events leading to the discontinuation of study drug will be generated.

Descriptive summaries of vital signs, clinical laboratory results, USP results, and the C-SSRS results will be presented by study visit and treatment group. The number and percentage of subjects with treatment-emergent clinical laboratory abnormalities will be summarized by treatment group. Normal range clinical laboratory shifts from baseline to end of study will be summarized by treatment group.

Concomitant medications will be coded using the World Health Organization (WHO) dictionary. These data will be summarized by treatment group. Previous and concomitant medications will be presented in a data listing.

Subject disposition will be presented for all subjects. The numbers of subjects who complete the study and who discontinue early from the study will be provided. The reasons for early discontinuation will also be presented.

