3.3. Summary of Statistical Analysis Changes to the Protocol

The analyses described in this analysis plan are consistent with the analyses described in the study protocol.

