4.2.2. Secondary Endpoints

Secondary endpoints include the following:

Safety and Tolerability:

- Adverse events
- Vital signs
- Clinical laboratory tests
- 12-lead electrocardiograms (ECGs)
- Urinary Symptom Profile - USP© questionnaire (USP)
- Columbia-Suicide Severity Rating Scale (C-SSRS)

Efficacy:

- Patient Global Impression of Change (PGIC)
- Expanded Disability Status Scale (EDSS)
- TNmAS – Total Limbs (TNmAS-TL)

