5.3. Analysis Variables

Variables to be analyzed include demographics and baseline characteristics, safety variables (adverse events, clinical laboratory investigations, vital signs, ECGs, USP questionnaire, and C-SSRS), and efficacy variables (TNmAS-MAL, CGIC, PGIC, EDSS, and TNmAS-TL). See Section 8 of the protocol for further details on the efficacy variables. Derived variables from study endpoints are described with the sections describing the analyses for these endpoints.

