7.4. Planned Study Analyses

7.4.1. Statistical Summaries: Descriptive and Inferential

All statistical tests will be two-sided and a difference resulting in a p-value of less than or equal to 0.05 will be considered statistically significant. All p-values will be rounded to and displayed in four decimals. If a p-value less than 0.0001 occurs it will be shown in tables as <0.0001.

Descriptive summaries of variables will be provided where appropriate. For continuous variables, the number of non-missing values (n) and the median, mean, standard deviation, minimum, and maximum will be tabulated by treatment. For categorical variables, the counts and proportions of each value will be tabulated by treatment. Expansion of descriptive table categories within each treatment may occur if such elaborations are thought to be useful.

For the summary statistics of all numerical variables unless otherwise specified, minimum and maximum will be displayed to the same level of precision as reported. Mean and median will be displayed to one level of precision greater than the data collected. The standard deviation / standard error will be displayed to two levels of precision greater than the data collected.

Change from baseline scores will be calculated as the post-baseline measurement minus the baseline value.

All collected data will be presented in listings. Data not subject to analysis according to this plan will not appear in any tables or figures but will be included in the data listings.

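### C-SSRS results are never tabulated by treatment group under the SAP, although Protocol 11.5 promises this and SAP 3.3 declares no departure

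*SAP*

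**What the plan says.** Protocol 11.5 (Safety Endpoints) promises: "Descriptive summaries of vital signs, clinical laboratory results, USP results, and the C-SSRS results will be presented by study visit and treatment group". The same section says that safety will be assessed descriptively, without statistical tests.

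SAP 10.6 (Other Safety Measures) gives C-SSRS one sentence: "C-SSRS results will be presented in subject data listings". After dealing with the urinary questionnaire (USP) and ECG, it closes the list: "No other safety analyses have been prospectively defined". Anything added later is treated as post hoc.

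SAP 7.4.1 puts all collected data in listings as a general rule, and adds: "Data not subject to analysis according to this plan will not appear in any tables or figures".

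SAP 3.3, where changes from the protocol would be declared, reads: "The analyses described in this analysis plan are consistent with the analyses described in the study protocol".

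SAP 4.2.2 nevertheless lists C-SSRS among the secondary safety and tolerability endpoints, and SAP 5.3 lists it among the variables to be analysed. Under Table 1 of either document it is collected at all six visits.

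**The concern.** The SAP is the document from which the tables are built. If it is followed as written, a by-arm safety output that the protocol specified will not be produced, and the study report will have no declared change to explain why.

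Safety is part of the stated primary objective. C-SSRS is also the only instrument in the trial that asks about suicidal ideation and behaviour in a structured way. A listing shows individual responses, but it does not state how many subjects in each arm were assessed at a visit, how many were positive, or how the arms compare. If a reviewer asks for those counts later, they will come from an analysis labelled post hoc, although the protocol had committed to it in advance.

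**Working it through.** No arithmetic is at issue, since the point depends on no rate, sample size or error level. The check is a comparison of texts.

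**Step 1. Follow each item in the Protocol 11.5 sentence into the SAP.**

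| Item | Protocol 11.5 | SAP |
|---|---|---|
| Vital signs | Descriptive summary by visit and arm | Descriptive summary by arm and time point (10.4) |
| Laboratory results | Same | Descriptive summary by arm and time point, plus shift tables (10.3) |
| USP | Same | Summary scores by arm and time point, plus listings (10.6) |
| C-SSRS | Same | Listings (10.6) |

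Three of the four items keep the promised summary. ECG is not in the protocol's sentence, yet SAP 10.6 summarises it by arm as well.

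**Step 2. Ask whether the C-SSRS sentence leaves room for a table.** It does not contain the word only, but three things close that reading.
- The USP and ECG entries in the same section name a summary and a listing separately. The C-SSRS entry names a listing alone.
- SAP 7.4.1 already lists all collected data, so SAP 10.6 gives C-SSRS nothing beyond that default. The same section keeps data without a planned analysis out of tables and figures.
- SAP 10.6 states that no further safety analyses are prospectively defined.

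**Step 3. Look for the table elsewhere.** SAP 4.2.2 and 5.3 name the variable but specify no output. SAP 8 and SAP 10.1 to 10.5 contain no C-SSRS output. Planned C-SSRS summary tables: none.

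**Step 4. Look for a declared change.** SAP 3.3 declares none. For C-SSRS its statement is incorrect.

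**Step 5. Ask whether the adverse event tables fill the gap.** SAP 10.1 tabulates TEAEs by arm and preferred term. SAP 10.2.2 and 10.2.3 do the same for serious events and for events leading to stopping or interrupting study drug. A positive C-SSRS response reaches those tables only if it is also reported as an adverse event.
- Protocol 9.7.1 elicits adverse events by general questions that must not suggest symptoms.
- Protocol 9.6.2 turns a defined rise in the USP score into an adverse event. Protocol 9.6.3 has no matching rule for C-SSRS.
- The adverse event tables are not by visit, so they would not meet the protocol's commitment even if every positive response were reported.

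**The case against.** A reader might infer that suicidality is never compared between the arms at all. The documents do not support that. Suicidal ideation or behaviour recorded as an adverse event is counted by arm under SAP 10.1, and again under SAP 10.2.2 or 10.2.3 if it is serious or leads to stopping or interrupting drug. Deaths receive listings and narratives under SAP 10.2.1. What stands is narrower: the C-SSRS data themselves are not tabulated by arm, and the adverse event route is partial for the reasons in step 5.

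A second objection is that little is lost. No safety tests are planned, every C-SSRS record stays in the listings, and SAP 8.1 reports the size of the Safety population by arm. Much of this is fair. The missing item is a descriptive display, and counts could be rebuilt from the listing with effort. The denominators for each visit would also have to be rebuilt, because SAP 8.1 gives only the population totals.

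A third objection is that SAP 5.1 calls the protocol the definitive reference, so the protocol's promise governs. That sentence sits in the design overview. Even if it is read broadly, the SAP would still lack the specification of a table that the protocol requires.

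A reader might also try to size the problem by the volume of assessments (510 × 6 = 3,060 at most) or by the upper limit that zero events in 170 subjects would give (1 − 0.025^(1/170) = 2.1%). Neither measures the defect. The first includes two visits, Screening and Baseline, that are not post-dose follow-up. The second assumes a result, and neither document plans confidence limits for safety data.

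**Conclusion.** The mismatch is real and undeclared. Protocol 11.5 promises C-SSRS summaries by visit and arm, SAP 10.6 drops them, and SAP 3.3 says that nothing has changed. The SAP is also at odds with itself, since it names C-SSRS as a variable to be analysed and then plans no analysis of it.

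The size is one descriptive safety output out of the four in the protocol's sentence. Data collection, the co-primary analyses, the testing order and the success criterion are untouched. It should be corrected because the correction is simple and the output was promised.

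The conclusion rests on two readings: that SAP 10.6 is complete as the list of planned C-SSRS outputs, which its own closing statement supports, and that no rule in the readable text of either document makes a positive C-SSRS response an adverse event. If such a rule exists elsewhere, the adverse event tables would capture more, but the promised by-visit summary would still be missing.

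**What to change.** In SAP 10.6, before unblinding, add a table on the Safety population, by visit and treatment group, of the number and percent of subjects with any suicidal ideation and with any suicidal behaviour. Use as the denominator the subjects assessed at that visit. Because Protocol 9.6.3 places non-suicidal self-injury within the behaviour construct, the table should say whether it is counted there or shown separately. Keep the listings.

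A row for any post-dose visit is optional, as it goes beyond what the protocol promised. A shift table is not needed to meet the commitment.

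With this table in place, the consistency statement in SAP 3.3 becomes true for C-SSRS. Declaring and justifying the omission in SAP 3.3 instead would make the change visible, but it would not restore the summary.

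The cost is one descriptive table. It needs no new data and has no effect on efficacy or on the type I error rate.

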11 REPORTING CONVENTIONS

The following reporting conventions will be adopted for the presentation of study data. These conventions will enhance the review process and help to standardize presentation with common notations

11.1 General Reporting Conventions

- All tables and data listings will be developed in Landscape Orientation, unless presented as part of the text in a CSR.
- Figures will be presented in Landscape Orientation, unless presented as part of the text in a CSR.
- Legends will be used for all figures with more than one variable or item displayed.
- Figures will be presented in color with treatment groups distinguished by different symbols and colors. Lines in figures should be wide enough to view the line after being photocopied.
- Specialized text styles, such as bolding, italics, borders, shading, superscripted

and subscripted text will not be used in tables, figures, and data listings unless they add significant value to the table, figure, or data listing.

- Only standard keyboard characters should be used in tables and data listings. Special characters, such as non-printable control characters, printer specific, or font specific characters, will not be used on a table, figure, or data listing. Hexadecimal character representations are allowed (e.g., μ , α , β).
- All titles will be centered on a page. The ICH numbering convention is to be used for all tables, figures, and data listings.
- All footnotes will be left justified and the bottom of a page. Footnotes must be present on the page where they are first referenced. Footnotes should be used sparingly and must add value to the table, figure, or data listing. If more than four footnote lines are planned then a cover page may be used to display footnotes.
- Missing values for both numeric and character variables will be presented as blanks in a table or data listing. A zero (0) may be used if appropriate to identify when the frequency of a variable is not observed.
- All date values will be presented as YYYY-MM-DD (e.g., 2013-05-17) ISO 8601 format.
- All observed time values will be presented using a 24-hour clock HH:MM:SS format (e.g., 01:35:45 or 11:26). Seconds should only be reported if they were measured as part of the study, also in ISO 8601 format.
- Time durations will be reported in mixed HHh MMm SSs notation (e.g., 5h 32m, or 27h 52m 31s). The use of decimal notation to present (display) time durations should be avoided (e.g. 0.083h = 5m) unless it is necessary to show the computation of time differences in a table, figure, or data listing, in which case both notations may be used to display the time duration.
- All tables, figures, and data listings will have the Table, Listing, or Graph status (DRAFT, FINAL), and a date/time stamp on the bottom of each output.
- All analysis programs developed for a table, figure, or data listing display will be self-contained to facilitate transfer of programs to multiple computing environments and transfer to a regulatory agency (if requested).

11.2 Population Summary Conventions

- Population(s) represented on the tables or data listings will be clearly identified in the last title of the Table as “Population: <name of population>” and will be identical in name to that identified in the protocol or SAP.
- Consistent terminology will be used to define and identify a population.
- Sub-population(s) or special population(s) descriptions will provide sufficient detail to ensure comprehension of the population (e.g., FAS Females, Per-

Protocol Males >60 years of age) used for analysis in a table or figure.

- Population sizes may be presented for each treatment or dosing category as totals in the column header as (N=xxxx), where appropriate.
- Population sizes shown with summary statistics are the samples sizes (n) of subjects with non-missing values.
- All population summaries for categorical variables will include all categories that were planned and for which the subjects may have had a response. Percentages corresponding to null categories (cells) will be suppressed.
- All population summaries for continuous variables will include: N, mean, SD, minimum, and maximum. Other summaries (e.g. number missing, median, quartiles, 5%, 95% intervals, CV or %CV) may be used as appropriate.
- All percentages are rounded and reported to xx.x%. A percentage of 100% will be reported as 100%. No value of 0% will be reported. Any computation of percent that results in 0% is to be presented as a blank.
- Population summaries that include p-values will report the p-value to four decimal places with a leading zero (0.0001). All p-values reported on default output from statistical software (i.e., SAS[®] Software version) may be reported at the default level of precision. P-values <0.0001 should be reported as <0.0001 not 0.0000.

